Summary:	
Early alcohol socialization occurs within the family. Our multi-level, high-reach, low-intensity intervention to prevent early alcohol use capitalizes on the influence of providers, immunization timing, and pediatric guidelines that advise healthcare providers to give anticipatory guidance about early alcohol use. In conjunction, the intervention capitalizes on the power of technology to reinforce and expand upon pediatrician messages.
 
Our study seeks to understand the feasibility and effectiveness of a pilot intervention designed to prevent alcohol socialization through education of parents of rising 6th grade students.

Objectives:	
To evaluate the feasibility and preliminary effectiveness of an intervention aiming to improve parents' attitudes about child alcohol use.

	
Primary outcome measure: The change in parents' score from an 8-item scale of pro-sipping beliefs from baseline to post-intervention (6 months).

Sample:	Parents of rising 6 th grade students.
Phase:	Phase 0/1 (Intervention development)
Participant duration:	Parents will participate in a text-based intervention for three months and complete surveys for up to 6 months after study enrollment. Children will complete one survey 3 months after study enrollment.
Description of intervention:	BIPAS Alcohol is an intervention intended to prevent early onset alcohol use by educating parents of rising middle schoolers. Parents will receive information delivered via text message for three months.
Estimated time to complete	

enrollment: 6 months

Schematic of study design:

BIPAS Alcohol intervention

2 INTRODUCTION: BACKGROUND INFORMATION AND SCIENTIFIC RATIONALE

2.1 2.1 Background information

Early initiation of alcohol use is a uniquely predictive risk for problematic alcohol involvement during late adolescence and adulthood. Prospective longitudinal studies show that children who have sips of alcohol during early adolescence, typically in the family context, are at higher risk for alcohol misuse, binge drinking and development of alcohol-related problems. Youth whose family context makes them more susceptible to drinking are also more likely to select into pro-alcohol peer groups that reinforce drinking attitudes and behavior. Alcohol misuse is the primary contributor to death by injury and is the leading cause of death for those under age 21. Alcohol use negatively alters brain development and is implicated in risky sexual behavior, aggressive and violent behavior, depression and social isolation, poor economic outcomes, smoking and other drug use, academic problems, and suicidality. Given the variety and magnitude of these negative consequences, early initiation of alcohol use is a major public health problem in need of public health interventions that have the potential for wide reach and high impact across the life course.

One quarter of 8th grade students and half of 10th grade students have already consumed alcohol. A significant minority of youth begin drinking even younger, and alcohol use rates double as children transition from elementary to middle school. Whereas only 10% of fourth graders have ever tried alcohol, more than 20% of sixth graders report ever drinking. Given this, and our finding that school transitions promote risk for onset of substance use, the transition to middle school is a critical period for prevention of alcohol initiation.

2.2 2.2 Rationale

Parents are the essential target of early intervention to prevent underage alcohol use initiation. A substantial body of evidence shows that permissive parental beliefs about alcohol, and concomitant permissive behaviors (e.g., permitted sipping of alcohol at home), are strongly associated with children's self-reported alcohol use. While peers become increasingly influential during adolescence, parents are more influential than peers for children and young adolescents. Additionally, parental attitudes shape how they monitor adolescent interactions with peers, so intervening with parents during early adolescence may also buffer negative peer influence. Our prospective analysis showed that, even in the context of other protective factors, adolescents whose parents had permissive beliefs about alcohol use exhibited quicker escalations in alcohol involvement across adolescence than those whose parents were less permissive about their children's alcohol use. Indeed, permissive parenting practices were more strongly predictive of growth in adolescent alcohol misuse than whether the parents themselves used alcohol heavily.

Text message-based interventions have been shown to be both acceptable and very effective across a variety of behaviors, including with parents. A meta-analysis of 19 RCTs of text message-based interventions found that tailored text messages are even more powerful for

promoting behavior change than un-tailored messages. Mobile phone ownership is near-universal in the United States (96% in 2019, including 99% of individuals aged 18-49). Importantly, mobile phone ownership rates are in the high-90s for Black, White, and Hispanic/Latino individuals.

2.3 2.3 Potential Risks and Benefits

2.3.1 2.3.1 Potential risks

Potential risks associated with participation for parents include loss of time and slight risk of embarrassment or discomfort in answering questions about their family practices around alcohol. However, because text message viewing is discretionary for parents, we expect loss of time to be minimal. All answers to survey questions and data received from text message usage will be kept confidential. Thus, the risk of embarrassment is anticipated to be very slight. Parents could become distressed about their own drinking behavior. We minimize these risks by tailoring the message content to parenting-related behaviors and offering resources on our website for parents seeking information about alcohol misuse.

We do not anticipate immediate or long-range risks associated with participation.

2.3.2 2.3.2 Known potential benefits

By participating in this study, parents will receive actionable information about incorporating alcohol discussions in their family life. This study will also help inform a future larger randomized control trial of the BIPAS Alcohol intervention.

3 OBJECTIVES

3.1 3.1 Study objectives

The purpose of this study is to evaluate the feasibility and preliminary effectiveness of BIPAS Alcohol, an intervention aiming to reduce pro-sipping beliefs, to encourage creation of clear, alcohol-specific rules, and to limit their provision of sips of alcohol to young adolescents.

3.2 3.2 Study outcome measures

Our primary outcome measure is changes in parents' self-reporting pro-sipping beliefs, attitudes, and practices at the end of the intervention period.

3.2.1 3.2.1 Primary outcome measures

For each participating parent, we will assess the change in composite score on an 8-item scale of self-reported pro-sipping beliefs, attitudes, and practices from baseline to 6 months (length of intervention). A four-point scale ranging from "strongly disagree" to "strongly agree" will be used, with higher values on the scale indicating a more pro-sipping belief system.

3.2.2 3.2.2 Other measures

No *a priori* secondary outcome measures.

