4 STUDY DESIGN

This study will evaluate the BIPAS Alcohol intervention with approximately 100 families. Parents will be randomized after enrollment into two groups: an intervention group and a waitlist-control group. Parents in the intervention group will begin receiving the intervention after enrollment, while parents in the waitlist-control group will receive the intervention three months after enrollment.

During the intervention period, all parents will receive text messages 2-3 times/week and online resources for three months about alcohol use and negative consequences in children, focusing on ways that they can create rules within the family environment to prevent alcohol use in children.

Parents in both groups will complete monthly surveys, and their child will complete one survey after three months. The parents in the intervention group will also receive a follow-up survey at 6 months. Parents in both groups will be asked if they would like to participate in an optional, follow-up qualitative interview about their experiences participating in the intervention.

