6 STUDY INTERVENTION

6.1 Study intervention description

The BIPAS Alcohol intervention offers education and tools to parents of children ages 10-12 about preventing early onset alcohol use through information delivered via text message. Parents will receive text messages on early onset alcohol use, negative effects, and evidence-based recommendations about encouraging discussion and rules with their child about alcohol. Text messages will be delivered 2-3 times/week for three months.

Parents will complete a baseline survey as well as monthly surveys about alcohol-related beliefs, knowledge, and behaviors. Parents in the intervention group will also complete a follow-up survey six months after enrollment.

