6.2 Dosage, preparation, and administration of study intervention

Each parent will receive text messages up to three times weekly and monthly surveys from our study team for a period of up to six months.

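### The primary outcome is read at 6 months, when the waitlist arm has either had the intervention or is not surveyed, so it has no untreated randomised comparator

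*Combined protocol and SAP*

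**What the plan says.** **Time point.** The protocol summary places the primary outcome "from baseline to post-intervention (6 months"). Section 3.2.1 gives the same endpoint as change in "pro-sipping beliefs, attitudes, and practices from baseline to 6 months (length of intervention"). Section 3.2 places it less specifically, at the close of the intervention period. No secondary outcomes are prespecified (section 3.2.2).

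**Design.** Section 4 randomises about 100 families to an intervention group or a waitlist-control group, and "parents in the waitlist-control group will receive the intervention three months after enrollment".

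**Programme length.** Section 6.1: "Text messages will be delivered 2-3 times/week for three months". The summary and section 4 also say three months. Section 3.2.1 equates 6 months with the length of the intervention, and section 6.2 describes texts and "monthly surveys from our study team for a period of up to six months".

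**Surveys.** Section 4 gives both groups monthly surveys without an end month. It then adds: "The parents in the intervention group will also receive a follow-up survey at 6 months". Section 6.1 repeats this: "Parents in the intervention group will also complete a follow-up survey six months after enrollment".

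**Analysis.** Section 8.4 models change over time by treatment arm and baseline characteristics in generalized linear mixed models, with multilevel multiple imputation. It names no time point for the arm contrast and does not mention the waitlist arm's crossover.

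**The concern.** A waitlist design gives a randomised comparison with no intervention only until the waitlist arm starts. Here that period ends at month 3, yet the primary outcome is read three months later.

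At 6 months the plan can yield one of two results. One is a pre-post change in the intervention arm alone, which cannot be separated from secular trend, repeat-survey effects or regression to the mean. The other is a comparison of immediate with delayed delivery, whose expected difference is near zero even if the programme works.

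Low power does not excuse this. Sections 8.2 and 8.4 say the estimates will be used to power a larger trial. A contrast pulled towards zero, or a pre-post change carrying other influences, would mislead that calculation. With no secondary outcomes prespecified, the month-3 contrast that the randomisation supports has no stated status.

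**Working it through.** **Step 1. Exposure by arm.** Inputs: programme length 3 months (summary, sections 4 and 6.1); intervention arm starts at month 0 and waitlist arm at month 3 (section 4). The fraction of the programme received by month m is min(m, 3)/3 in the intervention arm and max(m − 3, 0)/3 in the waitlist arm, for m from 0 to 6.

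| Month | Intervention | Waitlist | Difference |
|---|---|---|---|
| 0 | 0 | 0 | 0 |
| 1 | 1/3 | 0 | 1/3 |
| 2 | 2/3 | 0 | 2/3 |
| 3 | 1 | 0 | 1 |
| 4 | 1 | 1/3 | 2/3 |
| 5 | 1 | 2/3 | 1/3 |
| 6 | 1 | 1 | 0 |

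Month 3 is the last scheduled point with an untreated waitlist arm.

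**Step 2. The two readings of the survey schedule.**
- Waitlist surveys stop before month 6 (the natural reading of sections 4 and 6.1). There are then 0 control observations at the primary time point. Imputation cannot supply them, because no parent in either arm is observed untreated at month 6.
- Waitlist surveys run to month 6 (one reading of section 6.2). The control has then had the whole programme.

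Neither reading gives an untreated comparison.

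**Step 3. Expected contrast at month 6, in units of the full effect.**
- Effect builds over three months and holds: 1 − 1 = 0.
- Effect in the intervention arm fades to half by month 6: 0.5 − 1 = −0.5, which favours the control.
- Programme lasts six months, if section 3.2.1's label is taken literally, with a linear build-up: the waitlist arm has had 3/6 of it, so 1 − 0.5 = 0.5. The contrast is halved, and the comparator is still not untreated.

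**Step 4. Illustrative power.** The plan gives no alpha, power, effect size or SD, so its 100 parents cannot be reproduced. Assumptions: two-sided alpha 0.05, SD 1, 50 per arm, no dropout.

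Without baseline adjustment, SE = √(2/50) = 0.20. The effect detectable with 80% power is (1.960 + 0.842) × 0.20 = 0.56 SD (0.57 with the t distribution). Normal-approximation power, by true effect:

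| True effect (SD) | Untreated comparator | Contrast halved | Waitlist fully caught up |
|---|---|---|---|
| 0.3 | 32.3% | 11.7% | 5.0% |
| 0.5 | 70.5% | 24.0% | 5.0% |
| 0.8 | 97.9% | 51.6% | 5.0% |

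With baseline adjustment at correlation r, SE = 0.20 × √(1 − r²). For r = 0.6, SE = 0.20 × 0.8 = 0.16 and 0.5/0.16 = 3.125, giving power Φ(3.125 − 1.960) ≈ 88% (87% with the t distribution). A simulation of 4,000 runs with these values rejected in 86.5% at month 3 and 4.9% at month 6; a repeat gave 87.5% and 4.6%. As r goes from 0 to 0.7, t-based month-3 power runs from 69.7% to 93.4% for 0.5 SD and from 31.8% to 54.8% for 0.3 SD. When the waitlist arm has fully caught up, month-6 power equals alpha at every setting.

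**The case against.** **The mixed model could estimate a month-3 contrast.** Section 8.4 includes treatment arm and time, and both arms have monthly surveys, so the untreated months are in the data. The wording about each participating parent defines the outcome variable and does not by itself rule out a between-arm contrast. This stands as far as it goes. But section 8.4 names no contrast time, ignores the crossover and calls its estimates secondary. A single arm-by-time effect fitted through month 6 would mix treated and untreated waitlist time.

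**Section 3.2 points elsewhere.** The close of a three-month intervention period is month 3 for the intervention arm, where the contrast is clean. That suggests an inconsistency more than a deliberate choice. Section 3.2.1 and the summary, however, both specify 6 months.

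**A zero difference is conditional.** It needs a three-month programme and an effect that persists. Under a six-month programme the contrast would be diluted and not zero. This is correct, but the waitlist arm would still be partly treated.

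**The power figures rest on assumptions.** They do, and rejection at about 5% under a zero contrast is simply alpha. They illustrate the point; the conclusion follows from the schedule.

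**The fix may not be free.** No section says outright that the 8-item scale is in every monthly survey, and the only survey section 4 expressly dates to month 3 is the child's. Enrolment and data collection were set for 2023-2024, without masking. If data are already in hand, moving the primary time point is an endpoint change that needs a dated justification. These points stand and are carried into the fix.

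**Conclusion.** The concern holds. The primary outcome is fixed at 6 months in two places, and on neither reading of the survey schedule is there an untreated randomised comparator at that time. On a three-month programme with a persistent effect, the expected month-6 difference is 0. It is −0.5 of the effect if half fades in the intervention arm, and +0.5 of it if the programme instead lasts six months with a linear build-up. If the waitlist arm is not surveyed at month 6, there is no control value at all.

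This rests on the stated start times and durations; only the sizes depend on assumptions about build-up, persistence, correlation and effect. The fault lies in the endpoint's time point and not in the whole design, since months 0 to 3 are validly randomised. It must be corrected, because as written the primary outcome cannot estimate the effect of the intervention against no intervention.

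**What to change.** 1. In the summary and section 3.2.1, define the primary outcome as the between-arm difference in the 8-item score at 3 months, adjusted for baseline. Bring section 3.2 into line.
2. Require the waitlist arm's month-3 survey to be completed before its first text, and confirm that the 8-item scale is in that survey for both arms.
3. Carry the same contrast into section 8.4 as the primary analysis, and state how waitlist data after crossover are handled.
4. Keep the 6-month survey as a descriptive, within-arm durability measure, and state for each arm when surveys end.
5. Remove the parenthesis in section 3.2.1 that equates 6 months with the length of the intervention. Reconcile the statements of messaging duration in the summary and sections 3.2.1, 4, 6.1 and 6.2.

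**Cost.** Protocol wording, and the matching registration entry if it carries the same time point, plus a check on survey content and timing. No extra participants or instruments are needed if the scale is already in the month-3 survey. The headline becomes an end-of-programme effect and not a 6-month one. If outcome data have already been seen, the change should be dated, justified and reported as a change of primary endpoint.

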4 STUDY DESIGN

This study will evaluate the BIPAS Alcohol intervention with approximately 100 families. Parents will be randomized after enrollment into two groups: an intervention group and a waitlist-control group. Parents in the intervention group will begin receiving the intervention after enrollment, while parents in the waitlist-control group will receive the intervention three months after enrollment.

During the intervention period, all parents will receive text messages 2-3 times/week and online resources for three months about alcohol use and negative consequences in children, focusing on ways that they can create rules within the family environment to prevent alcohol use in children.

Parents in both groups will complete monthly surveys, and their child will complete one survey after three months. The parents in the intervention group will also receive a follow-up survey at 6 months. Parents in both groups will be asked if they would like to participate in an optional, follow-up qualitative interview about their experiences participating in the intervention.

5 STUDY ENROLLMENT AND WITHDRAWAL

5.1 Subject inclusion criteria

In order to be eligible to participate in this study, parents must:

- Be aged 18 or older;
- Be a parent or guardian of a child aged 10-12 years old;
- Cohabitate part-time (2 days/week) or more with enrolled child;
- Be able to complete study activities in English;
- Be able to give informed consent;
- Own a phone with text messaging capabilities and access to internet.

5.2 Subject exclusion criteria

Individuals will be excluded from participation if they do not meet study inclusion criteria. Additional exclusion criteria include: families in which the 10- to- 12- year-old child is actively receiving treatment for alcohol use disorder.

5.3 Strategies for recruitment and retention

Parents will primarily be recruited through flyers placed in elementary school electronic newsletters.

The risk of this research is minimal risk to participants. We affirm this study will be conducted in accordance with sound ethical principles. Potential participants will be fully informed about the details of the study and encouraged to ask questions or stop at any time.

5.4 Treatment assignment procedures

5.4.1 Randomization procedures

We will use a coin flip to determine which group parents will randomly be assigned to after enrollment.

5.4.2 Masking procedures

None.

5.4.3 Reasons for withdrawal

Participants who request to withdraw will be given the option to discontinue participation in the intervention. Participants who request to completely withdraw from the study will no longer be contacted.

5.4.4 Handling of withdrawals

See above.

5.4.5 Termination of study

Given the low-risk nature of this study, we do not anticipate grounds for premature termination.

6 STUDY INTERVENTION

6.1 Study intervention description

The BIPAS Alcohol intervention offers education and tools to parents of children ages 10-12 about preventing early onset alcohol use through information delivered via text message. Parents will receive text messages on early onset alcohol use, negative effects, and evidence-based recommendations about encouraging discussion and rules with their child about alcohol. Text messages will be delivered 2-3 times/week for three months.

Parents will complete a baseline survey as well as monthly surveys about alcohol-related beliefs, knowledge, and behaviors. Parents in the intervention group will also complete a follow-up survey six months after enrollment.

6.2 Dosage, preparation, and administration of study intervention

Each parent will receive text messages up to three times weekly and monthly surveys from our study team for a period of up to six months.

6.3 Modification of study intervention for a subject

Not applicable.

6.4 Accountability procedures for the study intervention

Not applicable.

6.5 Assessment of subject compliance with study intervention

Not applicable.

6.6 Concomitant medications/treatments

Not applicable.

7 STUDY SCHEDULE

7.1 Screening

Parents who are interested in participating will complete an online pre-screening questionnaire. Eligible families will be contacted by a member of the study team and confirm eligibility over the phone. Screening of interested families will be conducted prior to informed consent. After enrollment, study participants will be given a baseline survey and provided with additional study instructions. Successful completion of the baseline questionnaire will demonstrate a willingness and ability to participate.

7.2 Enrollment/baseline

Enrollment and data collection will occur in 2023-2024.

7.3 Follow-up

Not applicable.

7.4 Final study visit

Not applicable.

7.5 Early termination visit

Not applicable.

7.6 Unscheduled visit

Not applicable.

8 STATISTICAL CONSIDERATIONS

8.1 Study hypotheses

This is a feasibility trial designed to evaluate implementation outcomes and to obtain pilot data on efficacy of the intervention with a group of 100 parent-child dyads. We hypothesize that the BIPAS Alcohol intervention will increase parents' knowledge and decrease their pro-sipping behaviors around adolescent alcohol.

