8.2 Sample size considerations

We will test our hypothesis that the BIPAS Alcohol intervention will increase parents' knowledge and decrease pro-sipping behaviors with 100 parents of 10-to-12-year-old children. We acknowledge that our trial is underpowered to detect small differences or control for multiple testing. One purpose of this feasibility study is to estimate effect sizes for powering a large-scale RCT. By piloting our intervention in two clinics, our study is designed to provide the data needed to lay this groundwork.

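### The 6-month primary time point has no untreated control and no 3-month contrast is named; knowledge is also to be tested without a declared outcome

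*Combined protocol and SAP*

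**What the plan says.** **Primary outcome and time point.** The Summary measures change on the "8-item scale of pro-sipping beliefs from baseline to post-intervention (6 months"). Section 3.2.1 sets the same 6-month horizon: "For each participating parent, we will assess the change in composite score". It describes the scale more widely, as covering attitudes and practices as well as beliefs, and it equates 6 months with the length of the intervention. Section 3.2.2 declares no secondary outcomes.

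**Design.** Under section 4, parents are randomized to intervention or waitlist control, and the waitlist group starts the intervention three months after enrollment. The Summary and sections 4 and 6.1 give three months of texts. Both groups complete monthly surveys (section 4).

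**Who is surveyed at month 6.** Sections 4 and 6.1 assign the 6-month follow-up survey to the intervention group. The Summary has parents "complete surveys for up to 6 months after study enrollment", and 6.2 gives each parent monthly surveys for as long as six months.

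**Analysis and hypothesis.** Section 8.4 plans generalized linear mixed models of attitudes and behaviors over time by arm, calls these analyses secondary, and sends the estimates to later power calculations. Section 8.1 says: "We hypothesize that the BIPAS Alcohol intervention will increase parents' knowledge and decrease their pro-sipping behaviors around adolescent alcohol". Section 8.2 repeats it as a test: "We will test our hypothesis that the BIPAS Alcohol intervention will increase parents' knowledge and decrease pro-sipping behaviors". Section 6.1 lists knowledge among the survey topics.

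**The concern.** A waitlist design gives a comparison with no intervention only until the waitlist group starts. Here that is month 3, while the primary outcome is read at month 6. The randomized comparison the design was built to provide is therefore not the one declared primary.

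What is at stake is the pilot's stated product. Section 8.2 says one purpose is to estimate effect sizes for a large trial. An effect read at month 6 is either measured against parents who have been sent the same texts or not measured against anyone.

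The knowledge mismatch is smaller. A hypothesis to be tested, with no declared measure, time point or model, leaves the choice of score and survey open until the data are seen. The plan itself says "our trial is underpowered to detect small differences or control for multiple testing".

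**Working it through.** **Plan's own figure.** The only design figure is 100 parents. No alpha, power, effect size, SD or dropout is given, so it cannot be reproduced. The check is one of timeline and definition.

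**Step 1: timeline, from section 4 and the three-month texting period.**

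| Months | Intervention arm | Waitlist arm |
|---|---|---|
| 0–3 | receiving texts | untreated |
| 3–6 | follow-up | receiving texts |
| 6 (primary) | 3 months after texts end | 3 + 3 = 6, so texts are just ending |

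The last comparison with an untreated control is at month 3. This depends only on the waitlist start. It holds whether the intervention lasts three months (Summary, 4, 6.1) or six (3.2.1), a conflict that needs reconciling in its own right.

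**Step 2: what month 6 estimates.** Let d be the 3-month effect in SD units (positive favours the intervention), k the share of d the intervention arm keeps at month 6, w the waitlist arm's effect then as a share of d, and t the change that would occur without any intervention.

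- Both arms surveyed: (kd + t) − (wd + t) = d(k − w). Time trends cancel, but so does some or all of the effect.
- Intervention arm only: kd + t. Nothing in the data separates the two terms.

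If k and w each lie between 0.5 and 1 (assumed), the two-arm contrast runs from d(0.5 − 1) = −0.5d to d(1 − 0.5) = +0.5d, and is zero whenever k = w.

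**Step 3: consequence for sizing the larger trial.** Assume two-sided alpha 0.05 and 80% power: n per arm = 2(1.96 + 0.84)²/contrast² ≈ 15.70/contrast².

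- d = 0.5 (assumed), read at month 3: 15.70/0.25 = 62.8, so 63 per arm.
- Same d, read at month 6 with k = 1 and w = 0.5: contrast 0.25, and 15.70/0.0625 = 251.2, so 252 per arm.

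Halving the contrast quadruples the planned size.

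**Step 4: illustration within this trial.** Assume 40 per arm (80% of 50) and no baseline adjustment: SE = √(2/40) = 0.2236. The chance of a significant favourable result is 1 − Φ(1.96 − contrast/SE).

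| d | Month 3 | Month 6, k = 1, w = 0.5 | Month 6, k = w |
|---|---|---|---|
| 0.3 | 0.268 | 0.099 | 0.025 |
| 0.5 | 0.609 | 0.200 | 0.025 |
| 0.8 | 0.947 | 0.432 | 0.025 |

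With d = 0.5, k = 0.5 and w = 1, the contrast is −0.25. The chance of a significant favourable result is 0.001, and of one favouring waitlist 0.20.

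**Step 5: does 8.4 settle it?** The model uses repeated surveys and treatment arm, so with both arms' monthly surveys it contains months with an untreated control. It names no time point for the arm comparison and no term for the waitlist group's start of the intervention.

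**Step 6: knowledge, side by side.** Sections 8.1 and 8.2: to be tested. Section 6.1: surveyed. Sections 3.2.1 and 3.2.2: no outcome. Section 8.4: attitudes and behaviors only.

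**The case against.** The strongest reply is that controlled data exist. Both groups are surveyed monthly, and the estimates that 8.4 carries forward are mixed-model parameters, not a raw 6-month change. That stands. A reader might infer that the trial cannot estimate a controlled effect, and the documents do not support this. The fault is that the declared time point and the usable contrast differ and the latter is not named. Dilution or reversal follows only if the effect is read at month 6.

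A second reply is that the survey conflict is soft: an upper limit of six months is compatible with a 6-month survey for the intervention group alone, and the study schematic is not in the text available for review. This also stands, but either answer leaves month 6 without an untreated control.

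Third, this is a pilot: "This is a feasibility trial designed to evaluate implementation outcomes and to obtain pilot data on efficacy of the intervention". Significance probabilities fit such a trial poorly, so the table in the working is illustration only.

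On outcomes, several stronger inferences are tempting and unsupported:

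- *Behavior has no outcome.* The composite in 3.2.1 includes practices and 8.4 models behaviors. No section promises a separate behavior score.
- *The aim "to encourage creation of clear, alcohol-specific rules" is unmeasured.* The eight items are not shown, so this cannot be known.
- *Feasibility has no planned data.* Section 4 plans optional interviews on parents' experience. Defined feasibility measures are missing detail rather than a contradiction.
- *Knowledge is not collected.* Section 6.1 says it is surveyed.

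**Conclusion.** The timing point holds on the documents alone: at the primary time point there is no untreated control. The declared outcome is then either early against delayed intervention, worth d(k − w), or an uncontrolled change. An effect size read there could be diluted, zero, reversed or uncontrolled. Under the assumed range for k and w it lies between −0.5d and +0.5d. The values of d, k, w, retention, alpha and power are all assumptions; the conclusion needs only the month-3 waitlist start. The design is recoverable, because both groups' monthly surveys should supply a controlled month-3 comparison.

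The knowledge point also holds, but is minor: a stated test with no declared outcome or model. This should be corrected; it does not invalidate the trial.

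**What to change.** 1. **Primary analysis.** In 3.2.1 and 8.4, make the baseline-adjusted between-arm difference in the 8-item score at 3 months the primary analysis, as a named contrast in the planned mixed model and labelled primary. Have the month-3 survey completed before the first waitlist text. Keep the 6-month data as descriptive follow-up.
2. **Timing of the change.** Make and date it before outcome data are examined by arm. Section 7.2 places data collection in 2023–2024, so if the data have already been examined, report the 3-month contrast as post hoc.
3. **Reconcile** the Summary, 3.2.1, 4 and 6.1 on the length of the intervention; the Summary, 3.2.1, 4, 6.1 and 6.2 on who is surveyed at 6 months; and the Summary and 3.2.1 on what the scale measures.
4. **Knowledge.** Either declare the knowledge score as a 3-month secondary outcome, reported as an estimate with a 95% CI and no confirmatory test, or remove knowledge from the hypothesis in 8.1 and 8.2.

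Naming feasibility measures, such as enrollment and 3-month retention with CIs beside the planned interviews, is worthwhile but secondary.

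**Cost.** A protocol amendment and one named contrast, with no new data collection expected. The primary result would no longer address persistence to 6 months. Removing knowledge from the hypothesis is the cheaper choice under item 4, but gives up that claim.
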